D2C is a structural intervention designed to sustainably change the HIV care providers' practices and facilitate information exchange at the facility level. To address the implementation science questions by measuring the provider-level outcomes and avoid contamination of the control condition due to unblinded allocation of intervention at the patient level, we propose a cluster-randomized trial design for this pilot study and the prospective RCT. We will select eligible HIV clinics (see "Study Sites," above) and randomly assign them 1:1 either to the intervention or the control arms. To achieve greater comparability between the arms, we will match pairs of eligible sites based on organizational context factors derived from Aim 1 data analysis, including facility size and type (e.g., NGO vs. public clinic), service delivery structure (e.g., social workers vs. nurses), and existing services for HIV-positive PWID (e.g. Steps Toward Health) and will randomize within the pairs. This will minimize the degree of between-cluster variation within the groups and increase power and precision.

Randomization will be conducted by the data manager using a computer program.

Sample size

We used methodology from Hayes et al⁸⁴ to determine the effect size that the intervention needs to demonstrate in a feasible matched-pair randomized trial. We assumed the cluster size of 75 patients (based on the optimal case manager workload) with 5 clusters per arm (potentially manageable number given the existing research infrastructure in Ukraine), coefficient of variation between clusters within matched pairs equal to 0.15 (empirically estimated based on the data from 56 clinics in the ART OPTI study, see Previous Studies), power of 80% and 0.05 significance level. Proportion of participants re-engaging into ART within 3 months after inclusion into the study was used as the key outcome. Under the assumptions, the relative difference between the study arms should be at least 22% (e.g. 50% vs 72%). The adjacent chart shows the power and sample size of a pilot trial needed to detect this difference with 0.05 significance level. To achieve 80% power, we will need to recruit 160 participants, or 80 per arm. We propose to divide the sample equally between 4 sites (2 per arm) to test the matching procedures. We do not adjust for loss-to-follow-up because for our main outcomes (ART initiation, viral suppression), loss to follow-up is equal to not achieving the outcome.

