- use Acuity Tool to assess patient-identified financial, socioeconomic, and housing profiles and provide comprehensive internal or external referrals for supplemental or long-term resources;
- develop and implement personalized treatment plans for all clients based on the acuity assessments through existing case management programs;
- ensure accurate tracking and documentation of all interactions and activities with patients using the acuity tool and Tracking Module within the MIS;
- establish, develop, and maintain professional relationships with diverse treatment and service providers, including AIDS care, primary care, substance use, mental health, and social services;
- maintain current contact information using the Contact Information Form (Annex 0) and updates it at each visit.

Additionally, Case Managers assist Interviewers to schedule follow-up interviews (see below) in conjunction with the Intervention sessions (at 6 and 12 months).

Control Condition

Clinics randomized to the standard of care arm will continue to implement their client identification processes and case management as usual. One of the most common interventions with a focus on PWID is Steps Toward Health,⁸⁵ a case management program developed and tested through the PEPFAR-funded RESPOND project.^{8,86} It is theory-driven and standardized in manuals that contain background information, logic models, client assessment worksheets, step-by-step instructions for each session, and monitoring and evaluation guidelines. This 5-session intervention includes modules on self-care, HIV transmission risk reduction, drug treatment, and ART adherence. It does not include active outreach, client tracking, or tailored treatment components. Other possible interventions include Community-based Retention Intervention, Patients' School, and others.

Provision of these interventions (the fact of enrollment) will be recorded in the MIS by Recruiter, but the actual process data will not be collected.

Data Collection

Data on **primary outcomes** will be obtained from clinical records in the MIS and absence of data will be equal to not achieving the outcome, therefore the effective sample size will be exactly 160 patients. Data from the MIS will be extracted monthly (Annex 6). The primary outcomes are defined as:

- Engagement in HIV care: at least 3 clinical visits over at least 6 months within 12 months after study enrollment.

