- ART (re-)initiation: initiating or re-initiating ART within 3 months after study enrollment.
- ART adherence: the percentage of days in possession of medication (pharmacy refill gap method)⁸⁷
- HIV Viral Suppression: having at least one VL test with <200cp/ml and none with >=200cp/ml within 12 months after study enrollment.

Data on **secondary outcomes** will be collected using the patient survey at baseline, 6 and 12 months after enrollment. The secondary outcomes will include items in the following domains:

- Substance Use: Substance use battery from the Ukrainian IBBS studies, AUDIT-C; DAST-10 scale for addiction severity.
- Trust in Physician Scale
- Substance Use & HIV Stigma Mechanism Scales
- Readiness for Drug Treatment Scale
- Mental Health: PHQ-9
- Risk behaviors: Risk Behavior Assessment (RBA), modified for the drug use patterns of PWID in Ukraine. The RBA assesses drug use and sex-related HIV risk behaviors.
- Quality of life: Short Form-12 (SF-12), a global measure of patient quality of life; HRQoL, HIV-related quality of life
- Medical co-morbidities and engagement in ancillary care: (OAT, TB, STI and Hepatitis treatment) by self-report.

- HIV Treatment Satisfaction Questionnaire
- Patient-side cost questionnaire
- Socio-demographic information, including age, housing status, sex/gender, family/marital status, income, education, employment status.

The surveys will be administered by an experienced Interviewer, hired at each site. The questionnaire will be programmed using REDCap platform installed on a UIPHP server.

Intervention implementation

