We have powered this pilot study to evaluate feasibility of a prospective cluster RCT. The RCT will be considered feasible if the difference in the proportion of patients achieving the primary outcome (engagement in HIV care) will reach 22% between the study arms. We will estimate the impact of the intervention on the HIV care continuum using mixed effects models. For all outcomes, the data will have the same structure, with observations (t) nested within participants (i) nested within sites (j) nested within matched pairs (k). The correlations among observations will be addressed by using fixed-effects indicators for matched pair and normally distributed random intercepts for sites and for participants. Our mixed-effects models will include indicators for each of the two follow-up assessments, an indicator for site group assignment, and two group-assignment-by-follow-up interaction terms. We will also include sex/gender, age, and baseline covariates that have been identified in preliminary analyses as varying significantly across sites. A logit link function will be used for the primary outcome of ART (re-)initiation (defined above), and the coefficients for the two group-assignment-by-follow-up interaction terms will provide the estimates of the subject-specific intervention effects at 6 and 12 months post-baseline. We will examine the effects of sex/gender, age, substance use severity, ART history at baseline and other covariates in the multivariable models.

We will characterize patterns of behavior that impact HIV transmission (episodes of syringe sharing and episodes of unprotected intercourse in the prior 30 days without viral suppression) and we will use the same mixed-effects approach described above but with a log link function and negative

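### The effect on ART (re-)initiation is read from 6- and 12-month interaction terms, but the outcome is a single yes/no fixed at 3 months

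*Combined protocol and SAP*

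**What the plan says.** The Data Collection section defines ART (re-)initiation as "initiating or re-initiating ART within 3 months after study enrollment". The Sample size section uses the same quantity: "Proportion of participants re-engaging into ART within 3 months after inclusion into the study was used as the key outcome". It contrasts 50% with 72% and arrives at 160 patients, 80 per arm, at 4 sites (2 per arm). Data Collection also fixes one determinate value per patient for the primary outcomes: "absence of data will be equal to not achieving the outcome, therefore the effective sample size will be exactly 160 patients".

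The Statistical Analysis and Feasibility Assessment section gives every outcome the same structure, with repeated observations within participants, participants within sites and sites within matched pairs. The model has fixed matched-pair indicators, random intercepts for site and participant, indicators for the two follow-up assessments, "an indicator for site group assignment, and two group-assignment-by-follow-up interaction terms". It applies a logit link to ART (re-)initiation, refers back to the definition above, and adds that "the coefficients for the two group-assignment-by-follow-up interaction terms will provide the estimates of the subject-specific intervention effects at 6 and 12 months post-baseline".

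Two other primary outcomes are also single values. Engagement is "at least 3 clinical visits over at least 6 months within 12 months after study enrollment". Viral suppression is judged over the whole 12 months after enrollment. The baseline, 6- and 12-month schedule is that of the patient survey, which supplies the secondary outcomes.

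**The concern.** An outcome that is settled at 3 months has no separate baseline, 6-month and 12-month values. A group-by-visit interaction measures how the arm difference changes from the reference visit to a later one, so it has nothing to measure here. The plan does not say how the single value enters the repeated model, and the back-reference ties the model to the 3-month definition. No 3-month term or separate 3-month analysis is given.

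At stake is the model estimate for the outcome that sized the pilot. The analyst would have to choose a row layout, and that choice decides whether the named coefficients are zero, duplicated or not estimable.

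**Working it through.** **Inputs.** 50% vs 72%, 80 per arm, 4 sites (Sample size). 160 patients over 4 sites is 40 per site, so expected events are 0.50 × 40 = 20 per control site and 0.72 × 40 = 28.8 per intervention site. Model terms are from Statistical Analysis and Feasibility Assessment.

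**The plan's own figure.** For a two-sided 5% comparison of two independent proportions with 80% power, the mean proportion is 0.61 and

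n per arm = [1.96 × √(2 × 0.61 × 0.39) + 0.842 × √(0.50 × 0.50 + 0.72 × 0.28)]² / 0.22² ≈ 76.

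At 80 per arm, power is 82.0% by the normal approximation and 81.6% by exact enumeration of the uncorrected chi-square test. So 160 reproduces, approximately, as one between-arm comparison of one binary value per patient, with no cluster term. Two-sidedness is assumed; the plan does not state it.

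**Target effect.** log[(0.72/0.28)/(0.50/0.50)] = log 2.571 = 0.944, an odds ratio of 2.57.

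**The planned fixed part.** The columns are intercept, pair, group, visit 6, visit 12, group × visit 6 and group × visit 12, seven in all. Random intercepts and covariates are left out of this check. The logit was fitted to the expected counts under each possible layout.

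| Layout | Rank | Result |
|---|---|---|
| 6- and 12-month rows only | 5 of 7 | Visit 6 + visit 12 equals the intercept, and the two interactions sum to the group column. Keep group: one interaction is dropped and the other is 0.00. Drop group: both interactions are 0.944. |
| Baseline, 6 and 12; baseline coded 0 | 7 of 7 | Baseline is 0/80 in both arms, so the baseline log odds go to minus infinity and the fit separates. The interaction standard error is 3.5, 43 and 6,355 after 5, 10 and 20 Newton steps. |
| Value copied to baseline, 6 and 12 | 7 of 7 | Group 0.944; both interactions 0.000. |
| One row per patient (intercept, pair, group) | 3 of 3 | Group 0.944. |

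In the last layout the standard error, ignoring clustering, is √(1/40 + 1/40 + 1/57.6 + 1/22.4) = 0.335. The four denominators are the expected events and non-events per arm: 40 and 40, then 57.6 and 22.4.

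**Participant intercept.** With one binary record per patient, its variance cannot be estimated. With the value copied to several rows, responses never vary within a patient across the copied rows. The single-value outcome supplies no information for that term either way.

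**The case against.** The strongest defence is that ART status can vary over time. Primary-outcome data are extracted from the MIS every month, and the ordinal analysis of the care continuum uses ART use over the preceding 30 days. A repeated ART-status outcome would make the planned model estimable. That is correct, but the section does not name such an outcome; it refers back to the 3-month definition. Status at 6 or 12 months is also a different quantity from the one the pilot was sized on. Annex 6, cited for the extraction, is not in the text available for this review, so a row layout described there cannot be excluded.

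Second, the layouts above are possible readings that the plan does not state. In particular, nothing proposes copying a post-enrollment result to the baseline row. That stands. They are shown because the plan fixes no layout and none of them makes the full named set work.

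Third, a reader might infer that the named terms can never return the 3-month effect. That is too strong: with follow-up rows only and the group term dropped, each interaction equals 0.944. It is then the 3-month effect printed twice under the wrong months, in a model without the group indicator that the plan says it includes.

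Fourth, a reader might infer that the pilot's inputs to the full trial are compromised. The documents do not support this. The sizing works from arm proportions and a between-cluster coefficient of variation. The Study Design section lists effect size and coefficient of variation as the parameters to measure, and does not say that they come from these coefficients. Because absent data count as failure, the 3-month proportions by arm and site can be reported for all 160 patients.

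**Conclusion.** The concern holds as a mismatch between outcome and model. For ART (re-)initiation as defined, the full set of planned terms gives no usable 3-month effect: rank 5 of 7 with follow-up rows only, separation with baseline coded 0, and interactions of 0 when the value is copied to all rows. The target log odds ratio of 0.94 comes from the group term with one record per patient, or in duplicate and mislabelled if the group term is removed. Engagement and viral suppression are single 12-month values and do not fit the repeated structure either.

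The size of the problem is limited. It does not invalidate the 160 patients, the arm and site proportions, or the 22-point feasibility rule, which concerns engagement and is a difference in proportions. What is wrong is one specified model estimate in a pilot, which should be corrected before analysis. The numerical checks rest on the plan's 50% vs 72% with equal sites and cover the fixed part only. The 0.335 standard error ignores clustering and is not a forecast of the trial's precision.

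**What to change.** 1. For ART (re-)initiation at 3 months, and engagement and viral suppression at 12 months, state one record per patient. Keep group, matched pair, the planned site random intercept and the planned covariates. Remove the follow-up indicators, both interactions and the participant intercept. Take the effect from the group term.
2. For the same outcomes, also report the difference in proportions as the mean of the two within-pair site differences. This is on the scale used for the sizing and the feasibility rule.
3. Keep the time-by-group model for outcomes measured at baseline, 6 and 12 months, and limit the statement about all outcomes accordingly.
4. If 6- and 12-month ART effects are wanted, define a separate time-varying outcome, for example the 30-day ART use that already appears in the care-continuum stages.

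The cost is wording in the analysis section. Sample size, data collection and patient procedures do not change, and no information is lost because each of the three outcomes has one value per patient. Item 4, if taken up, adds one outcome to define. ART adherence, a percentage, is outside this point and needs its own model statement.

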binomial distribution. These analyses will provide parameters for estimating the rate of onward HIV transmission for the cost-threshold analysis. All analyses will include the use of the mixed effects "meqrlogit," "meologit," and "menbreg" procedures using Huber/White robust variance-covariance estimators. We will examine whether missingness is associated with observed data using standard methods.^{98–100} We will conduct a second set of outcome analyses using multiple imputation to evaluate the robustness of the primary outcome analyses to missingness and report estimates based on multiple imputation that would be valid based on the assumption that the data are missing at random (MAR). We will produce imputed datasets ($m > 10$) using chained equations,¹⁰¹ run outcome analyses on all sets, and derive point and standard error estimates for treatment effects and other parameters from the distribution of estimates from the outcome analyses with imputed datasets.

We will also evaluate the use of mixed proportional odds regression^{102,103} for determining whether intervention exposure is associated with an individual's location on five distinct stages of HIV care continuum: (1) not engaged in HIV care in the prior six months; (2) engaged in HIV care in the prior six months but no ART use in the prior 30 days; (3) ART use in the prior 30 days but no evidence of viral suppression in the prior 6 months; and (4) ART use in the prior 30 days with evidence of viral suppression in the prior 6 months. The HIV care continuum can be viewed as an ordinal categorical variable, and ordinal logistic regression will be used to evaluate if group assignment is associated with the location along the HIV care continuum. We will use the Score test to evaluate whether the proportional odds assumption of ordinal logistic regression.¹⁰⁴

These analyses will be essential for planning a full study. The findings will be used for sample size estimates, and data on HIV transmission risk will be used to determine whether the intervention could reasonably be cost-saving or cost-effective. This pilot analysis will provide important information on the feasibility of using ordinal logistic regression in a larger trial or in other analyses of the HIV care continuum.

Specific Aim 3a: To assess the feasibility, acceptability, and implementation-related processes and outcomes of the D2C strategy

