Effectiveness, medical costs, and QALYs: Few HIV prevention studies are sufficiently powered to directly measure reductions in infections, and we will estimate HIV incidence among sexual and injection-drug-using partners under the standard of care scenario and under the intervention scenario using Bernoulli process models¹¹⁶ of injection drug use and sexual intercourse with behavioral patterns based on participant assessments and HIV transmission probabilities based on an updated review of the literature. The model will be based on participant data with a one-year timeframe for intervention costs and HIV transmission, and we will incorporate literature-based estimates of lifetime treatment costs and QALYs associated with new HIV infections in Ukraine, discounted at 3% per annum.^{111,117} Differences between the scenarios in estimated HIV transmission are expected to be driven primarily by ART use, but we will also incorporate observed data on intercourse, condom use, injection drug use, syringe sharing, and partner characteristics. The primary model will be based on the point estimates of parameters, but we will also conduct sensitivity analyses where input parameters are sampled from distributions that capture the uncertainty in our estimates. Many modeling approaches are available for modeling the incremental cost-effectiveness of D2C; given the exploratory nature of the proposed research, we believe a Bernoulli process model is appropriate.

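### A missed follow-up interview removes a participant from the transmission-risk rates even when the MIS holds suppression status, so the rates given to the cost model may be too low

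*Combined protocol and SAP*

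**What the plan says.** Under Statistical Analysis and Feasibility Assessment, the transmission-risk outcome is "episodes of syringe sharing and episodes of unprotected intercourse in the prior 30 days without viral suppression". It uses the same mixed-effects structure as the other outcomes, with a log link and a negative binomial distribution. On its use the plan says: "These analyses will provide parameters for estimating the rate of onward HIV transmission for the cost-threshold analysis".

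The two parts of this outcome have different sources. Under Data Collection, risk behaviour (the RBA) belongs to the patient survey at baseline, 6 and 12 months. Viral suppression is a primary outcome taken from the MIS, which is extracted monthly. Absent MIS data count as failure, so all 160 participants are analysed. The Sample size section gives the same rule for the main outcomes: "loss to follow-up is equal to not achieving the outcome". No corresponding rule is given for the composite when an interview is missed.

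On missing data, the plan will examine whether missingness is associated with observed data. It will also run a second set of analyses by chained-equation multiple imputation under MAR, "to evaluate the robustness of the primary outcome analyses to missingness". No imputation predictors are listed. Specific Aim 3b takes behaviour patterns from participant assessments and says that scenario differences in transmission are "expected to be driven primarily by ART use".

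**The concern.** The composite can exceed zero only in someone who is not suppressed. If the people who miss interviews are disproportionately unsuppressed, the model describes risk among those still reachable, while Aim 3b needs the rate for the whole arm.

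The documents make selective response plausible. The baseline interview follows a clinic visit (First visit), interviewers are based at the sites (Data Collection), and follow-up interviews at intervention sites are scheduled alongside case-management sessions (Intervention Procedures). A specific effort to reach people who did not re-engage is described only for the qualitative interviews, of up to 20 participants (Specific Aim 3a).

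The random intercept for participants does not deal with this. Participants enrol after a missed visit, so their baseline counts may say little about who is later suppressed, and later suppression is not in the model. At stake are the onward-transmission inputs, and through them the infections averted and the cost-saving and cost-effective thresholds.

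**Working it through.** **The plan's nearest figure.** The documents give no interview response rates and no episode rates, so there is no figure for this outcome to reproduce. The nearest is the sample size, "we will need to recruit 160 participants, or 80 per arm", for 50% versus 72% at "power of 80% and 0.05 significance level". A two-sided pooled two-proportion formula gives (1.96 × √0.4758 + 0.8416 × √0.4516)² / 0.22² ≈ 76 per arm (152 in total). Power at 80 per arm is 82.0%. The 160 is therefore not matched exactly, but nothing below depends on it.

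**Inputs and assumptions**
- Unsuppressed share p: 50% control, 28% D2C. This borrows the plan's 50% versus 72%, which is stated for ART re-engagement, as a stand-in. A second case uses 72% versus 50%.
- Response if suppressed, rs, and if unsuppressed, ru: assumed, the same in both arms unless stated.
- Equal mean counts among the unsuppressed in both arms, so each arm's rate is proportional to its unsuppressed share.
- The suppression condition is read as applying to both types of episode.

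**Formula.** Share unsuppressed among respondents = p·ru / [p·ru + (1 − p)·rs].

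With rs = 0.90 and ru = 0.60:
- control: 0.300 / (0.300 + 0.450) = 0.400, true 0.500
- D2C: 0.168 / (0.168 + 0.648) = 0.206, true 0.280
- ratio: 0.515, true 0.560
- difference: 0.194, true 0.220

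| Unsuppressed, control / D2C | Response, suppressed / not | Respondent share, control / D2C | Bias in rates | Ratio (true) | Change in difference |
|---|---|---|---|---|---|
| 50% / 28% | 80% / 80% | 0.500 / 0.280 | 0 / 0 | 0.560 (0.560) | 0 |
| 50% / 28% | 90% / 80% | 0.471 / 0.257 | −6% / −8% | 0.546 (0.560) | −3% |
| 50% / 28% | 90% / 60% | 0.400 / 0.206 | −20% / −26% | 0.515 (0.560) | −12% |
| 50% / 28% | 90% / 50% | 0.357 / 0.178 | −29% / −37% | 0.497 (0.560) | −18% |
| 72% / 50% | 90% / 80% | 0.696 / 0.471 | −3% / −6% | 0.676 (0.694) | +2% |
| 72% / 50% | 90% / 60% | 0.632 / 0.400 | −12% / −20% | 0.633 (0.694) | +5% |

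**Equal overall retention.** Force 80% retention in each arm, with ru/rs = 0.667 and 50% versus 28% unsuppressed. The biases are still −20% and −26%.

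**Response differing by arm.** Keep rs = 0.90 and set ru = 0.75 in D2C and 0.50 in control. D2C is 0.210 / 0.858 = 0.245 and control is 0.250 / 0.700 = 0.357. The ratio is 0.69 against a true 0.56, so the error now runs against D2C.

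**Does imputation repair it?** A gamma-Poisson simulation used 400,000 per arm, a mean of 4 episodes if unsuppressed, later suppression independent of the baseline count, and response of 90% / 60%.

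| Analysis | Control | D2C | Ratio |
|---|---|---|---|
| Truth | 1.990 | 1.118 | 0.562 |
| Respondents only | 1.592 | 0.822 | 0.516 |
| MAR given baseline count | 1.592 | 0.822 | 0.516 |
| MAR given baseline count and MIS suppression | 1.987 | 1.118 | 0.563 |

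Under these assumptions, conditioning on the baseline count alone removes none of the bias. Adding MIS suppression removes it.

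**The case against.** The plan does have a missing-data strategy. It checks missingness against observed data and runs chained-equation imputation. Because the MIS outcomes are complete by definition, imputation has real work to do only on survey-based outcomes such as this one, so the authors may intend to cover it. The plan also does not say which set of estimates feeds Aim 3b. This much stands: it would be wrong to say the plan looks at respondents and nothing more, and baseline interviews are used in any case. It does not settle the matter. The imputation is described as a check on the primary outcomes, no MIS predictor is named, and imputation without suppression status need not help.

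A reader might infer that the rates are biased as a matter of fact. The documents do not show this. They give no response rate by suppression status, and the 400 UAH paid per completed questionnaire encourages response from everyone.

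A reader might also take the loss-to-follow-up rule to mean that everyone who misses an interview is unsuppressed. That rule scores MIS outcomes and says nothing about interviews. Someone can skip an interview and still have a viral load on record.

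Finally, the consequence may be modest. Aim 3b is exploratory and threshold-based, and ART use, its expected main driver, can be taken from the MIS for everyone. With 80 per arm, the suppression part alone gives SE(log ratio) = √(0.72/22.4 + 0.5/40) = 0.21 and a 95% CI of about 0.37 to 0.85 around 0.56, ignoring clustering and overdispersion. The move to 0.515 is about 0.4 SE. That limits the effect on a single estimate. However, sampling input parameters from their uncertainty distributions does not correct a systematic shift.

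**Conclusion.** The concern holds as a conditional one. The planned model discards suppression information that the MIS may already hold for non-respondents. If unsuppressed participants respond less often, both arm rates are too low even with identical response rules. At 90% versus 60% response and 50% versus 28% unsuppressed, the shortfalls are 20% (control) and 26% (D2C), with a ratio of 0.515 instead of 0.560. At 90% versus 80% they are 6% and 8%, with a ratio of 0.546. They are zero if response is unrelated to suppression and risk. All of this rests on assumed response rates, stand-in suppression levels and equal counts among the unsuppressed.

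A general claim that the error favours D2C is not supported. The absolute difference shrinks at 50% versus 28% unsuppressed and grows at 72% versus 50%. The ratio can move against D2C if response differs by arm, and the described procedures do differ: case managers help schedule interviews at intervention sites, while control sites rely on a contact form.

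**What to change.** In Statistical Analysis and Feasibility Assessment:

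1. State the source and window of suppression for this composite at 6 and 12 months, from the MIS, and how a window with no test is handled. The 6-month window already used for the care-continuum stages is one option. The primary definition is cumulative over 12 months and gives no 6-month status.
2. For non-respondents with MIS-documented suppression in that window, set the composite to zero.
3. For other non-respondents, impute the 30-day counts with the planned chained equations, using arm, site, baseline counts and MIS engagement, ART and viral-load status as predictors. Treat known death, transfer or imprisonment separately; otherwise imputed episodes would be assigned to people to whom they may not apply.
4. Name these estimates as the input to Aim 3b. Report the respondents-only analysis and a not-missing-at-random range as sensitivity analyses, and carry that range into the threshold runs.

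The cost is protocol wording and some extra analysis. Monthly MIS extraction and chained equations are already planned, so no new visits or data are needed. The main estimate would rest on missing at random given MIS status, and intervals may be wider.

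### Multiple imputation cannot test the three binary MIS primary outcomes, where absent data already count as failure, and the rule that no viral load test means not suppressed goes untested

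*Combined protocol and SAP*

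**What the plan says.** Three parts of the protocol bear on this.

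- **Sample size.** There is no allowance for dropout because, for ART initiation and viral suppression, "loss to follow-up is equal to not achieving the outcome".
- **Data Collection.** The rule is stated for all MIS-based primary outcomes: "absence of data will be equal to not achieving the outcome, therefore the effective sample size will be exactly 160 patients". Four outcomes are listed. Three are yes/no (engagement in care, ART (re-)initiation, viral suppression). The fourth, ART adherence, is a percentage. Viral suppression means "having at least one VL test with <200cp/ml and none with >=200cp/ml within 12 months after study enrollment", so a participant who is never tested cannot meet it.
- **Statistical Analysis and Feasibility Assessment.** A further round of analyses uses chained equations, more than ten imputed data sets and a missing-at-random (MAR) assumption. Its stated purpose is to "evaluate the robustness of the primary outcome analyses to missingness and report estimates based on multiple imputation". The section does not name the variables to be imputed, and does not say whether records coded as failures are set back to missing. It also plans adjusted models: "We will examine the effects of sex/gender, age, substance use severity, ART history at baseline and other covariates in the multivariable models".

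Secondary outcomes come from a survey at baseline, 6 and 12 months, with no failure rule. Under Protection Against Risks, participants may decline any question.

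**The concern.** The plan holds two rules for the same absent record. One turns it into a failure and makes that part of the outcome. The other treats absence as something to be imputed. For a binary MIS outcome both cannot apply at once, and the plan does not say which gives way. An analyst could run the imputation, change no outcome value, and report that the result is robust to missing data. Another could reset failures to missing and obtain a different answer under the same plan.

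The larger stake is viral suppression. Under failure coding, measured suppression depends on whether a test was done as well as on the virus. The Aim 3a section lists follow-up and coordination of tests among the processes of care that the intervention may influence. The quarterly benchmark reviews of MIS data are described for intervention sites. Under Control Condition, the commonest control programme is said to lack active outreach and tracking. Testing frequency could therefore differ by arm because of the intervention itself, and no planned analysis asks whether that drives the result.

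**Working it through.** **Step 1. The plan's own figures.** Inputs from the Sample size section: 50% vs 72%, 80% power, alpha 0.05 (taken as two-sided), 80 per arm. The simple two-proportion formula, ignoring clustering, gives

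n = [1.960 × √(2 × 0.61 × 0.39) + 0.842 × √(0.50 × 0.50 + 0.72 × 0.28)]² / 0.22² = 76 per arm, or 152 in total.

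With a continuity correction it is 85 per arm (170). At 80 per arm the uncorrected power is 82.0%. So 160 is not reproduced exactly, but it lies between the two results and equals 4 sites × 40. The point here does not depend on it. What matters is that dropout inflation is zero. If absent records were truly missing at 10%, 20% or 30% (assumed), 160 / (1 − d) gives 178, 200 or 229.

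**Step 2. Outcome values left to impute.** With absence coded as not achieved, each of the three binary outcomes has 160 of 160 values. Missing outcome values: 160 − 160 = 0.

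**Step 3. What undoing the coding would do.** Let p be the proportion achieving the outcome under failure coding and m the share of absent records in that arm. All absent records are failures, so imputing them at the observed rate of their own arm (the simplest MAR model, no covariates) gives p / (1 − m). Taking 50% vs 72% as a worked example, with m assumed:

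| Absent, control / D2C | Control | D2C | Difference (points) |
|---|---|---|---|
| 0% / 0% | 50.0% | 72.0% | 22.0 |
| 20% / 20% | 62.5% | 90.0% | 27.5 |
| 20% / 5% | 62.5% | 75.8% | 13.3 |
| 30% / 10% | 71.4% | 80.0% | 8.6 |
| 5% / 20% | 52.6% | 90.0% | 37.4 |

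The unstated choice can move the estimate a long way in either direction.

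**Step 4. Viral suppression and untested participants.** Let m now be the share without a VL test and s the assumed proportion of them who are suppressed. Compared with failure coding, the difference (D2C minus control) changes by m(D2C) × s(D2C) − m(control) × s(control). The Background gives about 74% undetectable among people who inject drugs and are on ART. It is used here only as a trial value for s; the testing shares are assumed.

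- Control 30%, D2C 15%: (0.15 − 0.30) × 0.74 = −11.1 points.
- Control 20%, D2C 10%: (0.10 − 0.20) × 0.74 = −7.4 points.
- Equal shares, same s: 0.
- The two unequal cases reversed: +11.1 and +7.4 points.
- Equal shares of 20%, s = 74% in control and an assumed 50% in D2C: 0.20 × 0.50 − 0.20 × 0.74 = −4.8 points.

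The last line shows that s has to be varied by arm: equal testing does not by itself remove the problem.

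**The case against.** Several counter-arguments are sound.

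- **Imputation has real work to do elsewhere.** Substance use severity comes from a survey in which items may be refused. A complete-case adjusted model would drop those participants, so imputing covariates could change even a primary estimate. Survey outcomes can be missing at 6 and 12 months. ART adherence is a percentage, and not achieving it has no stated value. A reader might infer that nothing at all is missing and that the primary results would be robust by construction. The documents do not support that: the zero in Step 2 covers the outcome values of the three binary measures only.
- **The word primary may mean the main set of analyses, for all outcomes.** That is a fair reading. It still includes the MIS outcomes, so the gap remains for them.
- **A sensitivity analysis may deliberately relax the main coding.** True, and the fix below does so. Imputing reset records would not contradict the plan if the plan declared it. It does not.
- **MAR need not give people out of care the success rate of those in care.** The imputation model could condition on MIS visits and refills. The plan neither includes nor excludes them, so the simple MAR model in Step 3 is one case.
- **More testing does not favour one arm for certain.** The suppression definition also fails anyone with a result at or above 200 cp/ml, so more tests mean more chances to fail.

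**Conclusion.** The point holds for the three binary MIS outcomes. Failure coding leaves no outcome value missing, so MAR imputation cannot test robustness to missing outcomes unless that coding is undone; the plan does not say it will be, and doing so would estimate a different outcome. The assumption that most needs a test, that an untested participant is not suppressed, has none.

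The size is unknown because the documents give no testing rates. The shifts of 7 to 11 points in Step 4 rest on assumed shares and on a 74% figure for people already on ART and undetectable, which is neither this population nor exactly this endpoint.

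A reader might set those shifts against the 22-point feasibility threshold and conclude that the feasibility decision is at risk. The documents do not support this: the threshold applies to engagement in care, and the planning figures concern ART re-engagement within 3 months. Neither needs a VL test.

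The main analysis, the outcome definitions and the 160 are unaffected. This is an inexpensive improvement worth making, particularly as the pilot's findings will feed the sample size of the full trial.

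**What to change.** In the Statistical Analysis section:

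1. Limit multiple imputation to survey outcomes and to survey covariates in the adjusted models.
2. Keep failure coding as the main analysis of the binary MIS outcomes.
3. State the adherence value for a participant with no refill record, which settles whether imputation is needed there.
4. Report the share without a VL test by arm.
5. Add a labelled sensitivity analysis of viral suppression. Treat as unknown those with MIS visits or dispensing but no VL test; leave other absent records as failures. Vary the assumed suppression separately by arm, in both directions, and report the values at which the conclusion changes.

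The cost is a few sentences of text and one small added analysis. The MIS data are already extracted monthly, so no new data collection or recruitment is needed.
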